6.6 Concomitant Medications/Treatments

Subjects may not be receiving treatment with another investigational drug within 30 days preceding the baseline visit and throughout participation in this study.

Chronic prophylactic use of antibiotics at enrollment is an exclusion criterion; however, if during the course of the study, the subject's PCP prescribes antibiotics (e.g., for treatment of otitis media), the Study Coordinator will record the medication on the Concomitant Medications Log. The study subject will receive the study drug application regardless of prescribed antibiotics by subject's PCP.

Concomitant medication use, including all prescription, over-the-counter medications, vitamins, and nutritional supplementation, will be recorded commencing with the screening visit and at each visit through completion of the study. All concomitant medications must be used according to the prescriber's instructions.

Fluoridated toothpaste will be provided under this protocol to all subjects.

7. Study Schedule/Procedures and Evaluations

Subject recruitment procedures:

- The study assistant or supervisor will make contact with the parent/caregiver through the Early Childhood Education Center (ECE) or at home. This individual will explain the study and obtain informed consent.
- The assistant will record the subject's age and sex and medical history based on parent/guardian report.
- The assistant will record concomitant medication use over the past 90 days.
- The informed consent packet will carry a pre-assigned subject number. If a parent does not consent, the reason will be recorded and the study number will not be used. If the family has a second child who is eligible, the study number shall be the same as the first child in the family enrolled, followed by the notation -2.

7.1 Baseline Visit

- The visit will be at the Center
- The examiner will conduct the baseline dental and oral examination.
- After the baseline visit, the study staff will record on lists of the subjects, the treatment code assigned by the statistician.

7.2 First Treatment Visit

- A study assistant will consult the student list and apply the assigned treatment.
- The study assistant will administer the Facial Images Scale, immediately following the varnish treatment.

7.3 Visits 2-8

- The visit will be at the Center
- The examiner will conduct the dental and oral examination at visits 4 and 8.
- A study assistant will retrieve the drug assignment and will apply the assigned agent
- The assistant will review and record concomitant medications
- The assistant will review and record adverse events

7.4 Follow-Up Contacts

The subject's teacher will be contacted 48 hours following treatment. If the child is not attending or the teacher knows of a problem, the parent will be contacted to determine if there is a reportable AE. The medical monitor will assign causality. No treatments will be done on Fridays to avoid having to make home visits in order to obtain the basic AE information on the weekend.

7.5 Premature Withdrawal

In the event of premature withdrawal from the study, the Premature Withdrawal (PW) visit procedures and evaluations should be completed whether or not the decision to withdraw is determined at a routine or unscheduled visit. If it is determined via telephone contact that a premature withdrawal will occur, the parent/guardian should be asked to bring the child in for a PW visit.

Activities to be completed include:

- The Examiner will conduct the Oral Soft Tissue exam
- The Examiner will conduct the caries exam
- The assistant will record concomitant medication use.
- The assistant will review and record on the AE Follow-Up Log the status of adverse events that are unresolved at the time of the premature withdrawal visit.

Premature withdrawal (including reports of subjects who are lost to follow up) should be reported to the Site Director within 24 hours of the site's knowledge of the event.

7.6 Unscheduled Visit

An unscheduled visit may be performed at any time during the study at the subject's request or as deemed necessary by the Principal Investigator. The date and reason for the unscheduled visit will be recorded in the subject's source documentation.

Activities to be completed include:

- The Examiner will conduct the Oral Soft Tissue exam
- The Examiner will conduct the caries exam
- The assistant will record concomitant medication use.
- The assistant will review and record on the AE Follow-Up Log the status of adverse events that are unresolved at the time of the unscheduled visit.

8. Assessments

[figure not shown]
8.1 Primary and Secondary Outcome Variables

Primary Outcome Variable

The primary outcome will be the surface-level primary molar caries increment ($d_{2-3}mfs/DMFS$) at two years post baseline, but the incremental dental caries at one year will also be compared between the two interventions. Only the statistician and sponsor will know of the one-year finding.

Secondary Outcome Variable:

Child response on the depicted Facial Image Scale (Buchanan & Niven, 2002) to the treatment will be recorded immediately after the initial treatment visit and after the fourth treatment visit.

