Exclusion Criteria	1. Known allergy to iodine 2. Known allergy to seafood 3. Known hypersensitivity to fluoride varnish 4. Diagnosis of thyroid disease 5. Chronic, prophylactic use of antibiotics

	6. Treatment with another investigational drug or other intervention within 30 days preceding the Baseline Visit.
Route and Dosage Form	Treatment applied to teeth topically (0.2 mL or control)
Primary Outcome Measures	Efficacy: Surface-level primary molar caries increment (d ₂ mfs) at 24- months post baseline
Secondary Outcome Measures	1. Safety: a. Adverse event occurrence 2. Child response (Facial Image Scale 1-5)
	The proposed sample size of 600 subjects will provide >90% power to demonstrate a 30% or greater reduction in caries in the test group as compared to the control varnish group.

Schematic of Study Design:

1. Key Roles

Individuals:	
Principal Investigator:	[name] Department of Oral Health Sciences University of Washington, Seattle Email: [contact]
Sponsor/Investigator:	[name] Professor of Oral Health Sciences University of Washington, Seattle Email: [contact]
Medical Monitor	[name] Pohnpei State Hospital Pohnpei, FSM
Regulatory Monitor:	[name] [name] Consulting, Inc. [name]
Site Director	[name], BDS Chief of Dental Division Pohnpei State Department of Health Services Pohnpei, FSM
Institution and Locations:	Pohnpei State Department of Health Services Pohnpei, FSM
Biostatistician	[name] Research Associate Professor of Oral Health Sciences University of Washington Seattle, WA Email: [contact]
Coordination Center	Regional Clinical Dental Research Center & Research Coordination Center Institute of Translational Health Sciences [name] [contact] / [contact]

2. Introduction: Background Information and Scientific Rationale

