3.2 Study Outcome Measures

3.2.1 Primary Outcome Measure

Surface-level primary molar caries increment (d₂mfs) at 24 months post baseline

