11.2 Sample Size Considerations

The primary outcome will be the surface-level primary molar caries increment ($d_{2-3mfs}/DMFS$) at two years post baseline, but the incremental dental caries at one year will also be compared between the two interventions. Based on the caries levels reported by [name] et al. (2010) and Chi et al. (2016) a conservative estimate for the coefficient of variation ($100 \times \text{standard deviation}/\text{mean}$) is 75%. Using a two-sided 0.025 significance level to control the type I error for testing at 1 and 2

years post baseline, 120 participants per intervention are required to demonstrate a 30% or greater reduction in caries in the test group as compared to the NaF varnish group with 90% power (van Belle and Martin, 1993; Champley, 2015). A 30% reduction by PVP-I + F⁻ versus NaF varnish alone was reported by Milgrom et al (2011) for any new caries (%), and a greater reduction would be expected in the amount of new caries in a high-risk caries population. To accommodate for attrition (up to 15%), although it is expected to be very low in the study population, a total of 280 participants will be enrolled.

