11.3 Statistical Analysis Plan

11.3.1 Primary Statistical Analysis.

The primary analysis will be conducted in accordance with the intention-to-treat principle, and multiple imputation procedures will be used to account for missing caries information (Schafer, 1997). For the primary outcome, incremental dental caries based on d₂₋₃mfs/DMFS, the unit of analysis will be the child and the mean dental caries increment will be compared between the two interventions separately at 1 and 2 years post baseline using a two-sample t test assuming unequal variances. This approach assumes the distribution of dental caries increment is approximately symmetrical, which is often true in high-risk caries populations. In this case, non-symmetry, log-linear regression using robust standard errors, which can accommodate count outcomes with skewed distribution, will be used to compare the caries rates between the two interventions (Hardin & Hilbe, 2003). Covariate-adjusted linear (or log-linear) regression models using robust standard errors will be used to compare dental caries increment, adjusting for baseline dental caries, stratification variables (education center and school), gender and age of the participant (Hardin and Hilbe, 2003). Analyses will be performed using R (The R Foundation for Statistical Computing, 2016; Version 3.3.0) and SAS (SAS Institute, Cary, NC, Version 9.4).

11.3.2 Analysis of Safety Data.

Adverse events (AEs) will be tabulated by treatment group, severity, and perceived relationship to investigational product. For each AE, treatment group comparisons regarding the occurrence of at least one event will be made using Fisher's exact tests. The comparisons will be repeated excluding all mild symptoms. Similar analyses will be performed after grouping AEs by body system using standard Medical Dictionary for Regulatory Activities (MedDRA) coding. Individual AEs will be listed, with particular attention paid to serious AEs.

11.3.3 Participant Disposition.

The frequency and reasons for withdrawal will be summarized by treatment group, as will the number of missed visits and missed treatment applications (compliance).

12. Source Documents and Access to Source Data/Documents

The site will maintain appropriate medical and research records for this trial, in compliance with ICH E6, Section 4.9 and regulatory and institutional requirements for the protection of confidentiality of subjects.

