13.3 Amendments

The Principal Investigator will discuss any proposed protocol changes with the Sponsor and no modifications will be made without prior written approval and WIRB approval of the amended protocol, except where clinical judgment requires an immediate change for reasons of subject welfare. The WIRB will be informed of any amendments to the protocol or consent form, and approval (where and when appropriate) will be obtained before implementation.

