14.4 Timing/Reports

Enrollments and **study activity (protocol-specified reportable events)**, as described in Section 9.6.1) reports will be generated as they occur to a pre-determined distribution list that includes the Principal Investigator and team.

Clinical monitoring reports will be generated periodically with electronic distribution to the PI and team. Per the Clinical Monitoring Plan, the clinical monitor reports include routine reports of aggregate, blinded adverse event data for ongoing review by for potential trends, and adverse event and concomitant medication reports for the PI to review for standardization of coding.

Safety monitoring reports will be provided by the Biostatistician per the safety monitoring plan.

Missing data, missing electronic signatures of the Principal Investigator, and requests for **data clarification** reports will be generated to the site on a regular basis.

Monitoring Visit Reports will be generated after each clinical site monitoring visit, per the monitoring plan.

At the completion of the study, data will be securely transferred to the Biostatistician. Once the Biostatistician and the PI agree that all queries have been adequately resolved and the database has been deemed “clean”, the database will be officially signed off and deemed locked. All permissions to make changes (append, delete, modify or update) the database are removed at this time.

All site personnel, Sponsor and staff will remain blinded as to treatment assignments until the conclusion of the entire study. A designated unblinded biostatistician will have access to the treatment assignments, and this individual will not communicate about study-related matters to any other staff involved in the study. The study code will be broken by the study-responsible statistician after all outstanding substantive data queries have been resolved.

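### The primary endpoint is stated inconsistently: a primary-molar d2mfs increment in the Protocol Summary and 3.2.1, but with /DMFS added in 8.1, 11.2 and 11.3.1, and no tooth restriction in 11.3.1

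*Combined protocol and SAP*

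**What the plan says.** Five places in the combined protocol and SAP state the primary outcome.

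- Protocol Summary, Primary Outcome Measures: "Efficacy: Surface-level primary molar caries increment", with d2mfs in brackets, at 24 months.
- Section 3.2.1: "Surface-level primary molar caries increment (d₂mfs) at 24 months post baseline".
- Section 8.1: "The primary outcome will be the surface-level primary molar caries increment ($d_{2-3}mfs/DMFS$) at two years post baseline".
- Section 11.2: "The primary outcome will be the surface-level primary molar caries increment ($d_{2-3mfs}/DMFS$) at two years post baseline".
- Section 11.3.1: "For the primary outcome, incremental dental caries based on d₂₋₃mfs/DMFS", with the child as the unit of analysis and no mention of primary molars.

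Neither index is defined in the visible text, and the list of abbreviations as shown has neither. Section 8.2.1 refers to external examination criteria without saying which teeth or which lesion threshold count. The addendum (section 17) concerns the age range only. The objective in 3.1 speaks of new caries lesions without naming teeth, so it does not settle the matter.

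**The concern.** A trial needs one primary endpoint, fixed before anyone sees comparative data. Here, one analyst who follows 3.2.1 and another who follows 11.3.1 could each comply with the protocol and still compute different increments for the same child. The mean difference, its variance and the p-value could all differ.

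The same outcome is also compared at one year (8.1 and 11.3.1), so the ambiguity affects both planned tests. If the definition is settled only after the one-year comparison, the sponsor can no longer show that the choice was independent of the data.

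**Working it through.** **1. The five statements side by side**

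| Place | Tooth words | Index |
|---|---|---|
| Protocol Summary | primary molar | d2mfs |
| 3.2.1 | primary molar | d2mfs |
| 8.1 | primary molar | d2-3mfs/DMFS |
| 11.2 | primary molar | d2-3mfs/DMFS |
| 11.3.1 | none | d2-3mfs/DMFS |

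Four of the five name primary molars, and three of the five carry /DMFS. The change from d2 to d2-3 may be notation only, if d2 means that grade or worse; the documents do not say. The firm discrepancies are /DMFS and the missing restriction in 11.3.1.

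**2. What each version counts**

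For one child, let *a* be the new affected surfaces on primary molars, *b* those on permanent teeth and *c* those on other primary teeth.

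- Summary and 3.2.1: *a*.
- 8.1 and 11.2: *a* by the words; by the index, *b* enters as well.
- 11.3.1, if the slash means a sum: *a* + *b* + *c*.

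The slash could also mean either index or two separate outcomes. Under the sum reading, 11.3.1 exceeds 3.2.1 by *b* + *c*. The two agree for a child only when that total is zero.

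**3. Can *b* be non-zero at the primary assessment?**

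- Entry age is 48 to 84 months (5.2). At 24 months: 48 + 24 = 72 and 84 + 24 = 108 months, about 6 to 9 years. With the Summary's lower limit of 60 months, the youngest is 60 + 24 = 84 months.
- The last examination is at visit 8 (7.3), with applications every 3 to 4 months (6.2). If visit 1 is at month 0, visit 8 falls between 7 × 3 = 21 and 7 × 4 = 28 months. The youngest child could then be 48 + 21 = 69 months, so not every child is certain to be six.
- Section 2.1 describes first permanent molars erupting in children five to six years old.

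Permanent teeth can therefore be present in this age range, and the versions can differ in practice.

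**4. Is the sample size tied to one version?**

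The figure in 11.2 reproduces. With a 75% coefficient of variation (CV) in both arms, a 30% reduction, two-sided 0.025 and 90% power:

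n = (2.2414 + 1.2816)² × 0.75² × (1 + 0.70²) / 0.30² = 12.41 × 0.5625 × 16.56 ≈ 115.6, so 116 per arm.

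A Welch t calculation gives 117. The plan states 120, where power is 90.8%. The arithmetic is sound, but the CV is not attached to an index. The 30% comes from a study that section 2.1 describes as being in the primary dentition of children aged 12 to 30 months. By 11.2's own account it was reported for any new caries as a percentage, not as a surface count.

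The CV of the chosen index matters, as this illustration shows. Values other than 75% are assumptions, not from the documents, and the true value could also be lower. The 300 per arm is half of the maximum enrolment of 600.

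| CV | Power, 120 per arm | Power, 300 per arm |
|---|---|---|
| 75% | 91% | over 99% |
| 90% | 77% | 99% |
| 100% | 67% | 98% |
| 125% | 46% | 88% |
| 150% | 32% | 72% |

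**The case against.** The best defence is that four of the five places name primary molars. If the words control, /DMFS adds nothing, because primary molars have no permanent-tooth surfaces, and those four places then agree on the teeth. Section 11.3.1 may be shorthand for 8.1 and 11.2. The documents never define DMFS, so reading it as permanent teeth relies on standard notation. Scoring criteria (8.2.1) and data-handling conventions (14.1) are kept in other documents that may hold a workable definition.

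This correctly narrows the point, and it would be wrong to say that the later sections abandon the primary-molar limit. It does not remove the point. No passage says that the words control. The added index appears three times, including in both statistical sections. External scoring rules would not repair a protocol that contradicts itself on its primary endpoint.

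Two stronger readings are tempting but not supported.

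- A reader might infer an inflated type I error, from computing both versions and keeping the better one. No passage plans that. Section 13.3 says "no modifications will be made without prior written approval and WIRB approval of the amended protocol", and 14.4 keeps the sponsor and staff blinded to assignments. Any inflation would also depend on an unknown correlation between the versions.
- A reader might infer that the sponsor will choose with unblinded results in hand, because 8.1 says "Only the statistician and sponsor will know of the one-year finding" while 14.4 says "All site personnel, Sponsor and staff will remain blinded as to treatment assignments until the conclusion of the entire study". One statement concerns a finding and the other concerns assignments. The products are coded A and B, so a result shown by coded arm could satisfy both. Who sees the one-year result is a separate question, and this point does not rest on it.

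**Conclusion.** The point holds as an internal contradiction in the primary endpoint and must be corrected. In 8.1 and 11.2 the index conflicts with the words *primary molar*; in 11.3.1 the restriction is absent. The visible text does not say which version governs.

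Confidence in the textual mismatch is high. The size of its effect on the result is unknown, because the documents give no data on permanent-tooth or other primary-tooth increments. The conclusion rests on the standard meaning of DMFS and on permanent teeth being present at about 6 to 9 years, which section 2.1 supports. The power figures show only why the planning inputs need checking. They do not show that the trial is underpowered.

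**What to change.** Before the one-year comparison and before unblinding, choose one tooth set, index and lesion threshold, and state them in the same words in the Protocol Summary, 3.2.1, 8.1, 11.2 and 11.3.1. Either option below would be consistent.

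- **Simplest:** keep the primary-molar index of the Summary and 3.2.1, delete /DMFS from 8.1, 11.2 and 11.3.1, add the primary-molar restriction to 11.3.1, and report any DMFS increment as a separate, non-primary outcome.
- **If permanent teeth are meant to count:** delete the primary-molar restriction wherever it appears, and state in all five places that the endpoint is the sum of the dmfs and DMFS increments.

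Under either option, say whether d2 and d2-3 mean the same threshold. State how erupting and exfoliated teeth are handled, or cross-refer to the document that does so. Confirm that the 75% CV and the 30% effect in 11.2 apply to the chosen index, and redo the calculation if they do not.

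The cost is low: an amendment to five short passages, a check of two planning inputs, and a check that the examination form records the teeth needed. If all teeth are already charted, no visit or assessment is added.

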5.7 Masking Procedures

All study personnel except for designated personnel in the data center will be blinded to the participant treatment assignment. In order to maintain blinding, the caries scoring examinations will precede the application of test varnishes at baseline. The staff member applying these varnishes will not perform the caries scoring exams in order to eliminate examiner bias and ensure blinding to treatment assignment.

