6.1.2 Formulation, Packaging, and Labeling

Advantage Anti-Caries Varnish. The active ingredients are 10% (w/v) Povidone Iodine CAS RN 25655-41-8 and 5% (w/v) Sodium Fluoride CAS RN 7681-49-4 in Ethanol 200 Proof. The formulation of the dosage form includes 10% Nt-2 Premium Shellac, 1% sodium phosphate, dibasic anhydrous, 0.5% ammonium phosphate, monobasic, and 1% caramel cream flavor (Bell 29.26303) as inactive ingredients. One and two-year shelf life of the varnish has been established according to Guidance for Industry Q1A(R2) Stability Testing of New Drug Substances and Products (Revision 2, November 2003).

The active control varnish will be the same fluoride varnish without iodine with an appropriate FDA approved food dye added to match the color of the test agent. There will be no difference in the treatment and control varnishes except for the povidone iodine.

The varnishes will be packaged in 12 mL multi use bottles with the following labeling.

Advantage Anti Cavity Varnish or Control Varnish

- Apply as per protocol
- For Investigational Use Only
- Drug Code A or B
- Contact: [name], [contact] (24 hours)

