14.1 Data Management Responsibilities

The Biostatistician will be responsible for all data collection procedures. The Data Management Plan includes, but is not limited to:

- Overview of data management processes utilized for study
- Universal data handling conventions
- Study-specific data handling conventions
- Coding dictionaries and practices
- Specifications for logic and edit checks
- External data handling practices
- Final study closeout activities
- Audit plans
- Sample CRF annotation
- Biostatistician contact information
- Section for tracking revisions to the plan
- Administrative report specifications

The Data Management Plan serves to document the practices and procedures deployed to promote consistent, efficient, and effective data management practices leading to the creation of a high-quality database ready for analysis. The plan serves as the authoritative source, documenting data management practices, and decisions that are agreed to with the Principal Investigator at the start of the study and as necessary updates are made during the conduct of the study.

Data will be transferred periodically from the study site to the University of Washington to prepare reports. At the close of the study, the locked database will be transferred to the Biostatistician for analysis.

The Biostatistician will be responsible for design of the randomization scheme, creation of analytical databases, and the statistical analysis plan.

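### Section 8.1 lets the sponsor know the one-year between-arm caries result, while 14.4 blinds the Sponsor to study end; when, how and why the sponsor receives it is not stated

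*Combined protocol and SAP*

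**What the plan says.** **Access.** Section 8.1 names the two-year increment as primary, has the one-year increment compared between the interventions as well, and then says "Only the statistician and sponsor will know of the one-year finding". The roles table in Section 1 lists the sponsor as Sponsor/Investigator, in a row separate from the Principal Investigator.

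**Blinding.** Section 14.4 says "All site personnel, Sponsor and staff will remain blinded as to treatment assignments until the conclusion of the entire study". A designated unblinded biostatistician holds the assignments, and "this individual will not communicate about study-related matters to any other staff involved in the study". On unblinding, the same section says "The study code will be broken by the study-responsible statistician after all outstanding substantive data queries have been resolved". Section 5.7 gives the general rule: "All study personnel except for designated personnel in the data center will be blinded to the participant treatment assignment".

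**Timing.** Section 14.1 says "At the close of the study, the locked database will be transferred to the Biostatistician for analysis", but also "Data will be transferred periodically from the study site to the University of Washington to prepare reports".

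**Status of the one-year test.** Section 11.2 gives it a two-sided 0.025 level, and 11.3.1 gives it a method, an unequal-variance t test. The table of contents lists planned interim analyses as 11.3. In the body, 11.3 is the statistical analysis plan and there is no interim section.

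**Codes.** Bottles are labelled "Drug Code A or B" (6.1.2), and the envelopes in 5.6.2 use the same two letters for the whole trial.

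**The concern.** Section 8.1 makes the sponsor one of two parties who know how the arms compare at one year. Section 14.4 is written as though the sponsor learns nothing about treatment until the end. The text does not say which governs, and the section that might have settled it is absent from the body.

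The timing matters. After baseline, caries is examined at visits 4 and 8 (7.3). When the one-year data exist, visits 5 to 8, about half of the 24-month treatment period, and the primary examination are still ahead. In that time the sponsor may discontinue the study at its discretion (5.9), decides whether to halt it on safety grounds (9.9), and is consulted on protocol changes (13.3). If the sponsor has seen the one-year comparison, nobody can later show that such a decision was taken without knowledge of the efficacy trend. Written reasons for termination (5.9) and IRB approval of amendments (13.3) record and review a decision. They do not show what the decision-maker knew.

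**Working it through.** **1. The plan's own sample size, to confirm the inputs.** Section 11.2 gives a CV of 75%, a 30% reduction, two-sided 0.025, 90% power and 120 per arm. With the same CV in both arms and the control mean set to 1:

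n per arm = (z₀.₉₈₇₅ + z₀.₉₀)² × CV² × (1 + 0.7²) / 0.30² = (2.2414 + 1.2816)² × 0.5625 × 1.49 / 0.09 = 115.6, so 116.

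The noncentral-t version gives 117, and power at 120 is 90.8%. The plan's 120 is reproduced.

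**2. Type I error.** 0.025 + 0.025 = 0.05. The one-year test is already paid for.

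**3. Possible readings of the 8.1 sentence.**

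| Reading | Consequence |
|---|---|
| Comparison run only after lock, as 14.1 suggests | No conflict with 14.4, but the limit on who knows the result then has little function |
| Released before study end, labelled by arm | The sponsor knows which varnish is ahead while the trial runs, which defeats the purpose of the 14.4 blinding |
| Released before study end, labelled A and B | May not breach the wording of 14.4, which speaks of assignments; what it reveals is computed in step 4 |

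**4. What a coded result would reveal.** With two trial-wide codes, the question is how often the code with the lower mean increment is the test varnish. For a true proportional reduction r, the same CV in both arms and n completers per arm:

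z = r / (CV × √[(1 + (1 − r)²) / n]), and P = Φ(z).

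Completers per arm after 15% attrition (11.2):
- 280 enrolled (11.2): 280 × 0.85 / 2 = 119.
- 600 enrolled (the upper figure in 5.1): 600 × 0.85 / 2 = 255.

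Worked case, CV 0.75, r = 0.30, n = 119: the standard error is 0.75 × √(1.49 / 119) = 0.0839, z = 0.30 / 0.0839 = 3.57, and P = 99.98%.

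| CV | True reduction | P at 119 per arm | P at 255 per arm |
|---|---|---|---|
| 75% (plan) | 30% (plan) | 99.98% | >99.99% |
| 75% | 20% (assumed) | 98.8% | 99.96% |
| 75% | 10% (assumed) | 86.0% | 94.3% |
| 150% (assumed) | 30% | 96.3% | 99.6% |
| 150% (assumed) | 20% (assumed) | 87.2% | 95.2% |
| 150% (assumed) | 10% (assumed) | 70.6% | 78.6% |
| any | none | 50% | 50% |

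Section 11.2 gives no separate one-year CV or effect, so using its figures at one year is itself an assumption. A check with skewed counts (negative binomial, assumed control mean of 6, 40,000 simulated trials) agreed: at 119 per arm it gave 0.9999 for CV 75% with a 30% reduction, and 0.708 for CV 150% with a 10% reduction.

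**The case against.** The strongest reply is that 8.1 and 14.4 do not literally contradict each other. Section 14.4 blinds the Sponsor to assignments and 5.7 blinds personnel to each participant's assignment, whereas 8.1 concerns an aggregate finding. Section 8.1 can be read as a deliberate, specific access rule beside a general one. That stands as a matter of wording. It does not make the sponsor's knowledge of the trend harmless, and it leaves date, form and use unstated.

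Several stronger readings are tempting, and the documents do not support them:

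- **That 14.4 forbids the biostatistician to tell the sponsor.** The bar covers communication with other staff, and the same paragraph lists the Sponsor apart from staff. It is ambiguous here.
- **That 14.1 forbids any analysis before lock.** It places the transfer for analysis at study close but also allows periodic transfers for reports. It does not exclude an earlier comparison.
- **That the one-year comparison has no purpose.** It is a planned test with its own level and method. Only the purpose of the sponsor's access is missing.
- **That the sponsor receives child-level code lists, or is the person scoring or treating.** No section shows this. Names are removed, so whether the Sponsor/Investigator and the Principal Investigator are one person cannot be checked. Section 5.7 separates caries scoring from varnish application.
- **That 99.98% measures harm.** It assumes a coded release, which no section specifies, and a real one-year effect. With no effect it falls to 50%.

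**Conclusion.** The point holds as a conflict of purpose between 8.1 and 14.4 that the documents leave unresolved. Followed as written, 8.1 lets a sponsor with power over the trial's continuation know the between-arm efficacy trend, quite possibly while half the treatment period and the primary examination remain. Labelling by code would protect little if the effect is anywhere near the planned one. At 119 per arm, the better-looking code is the test varnish with probability 99.98% under the plan's assumptions, 71% at the weakest non-null case examined, and 50% under no effect.

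These probabilities describe information released. The documents do not allow any resulting bias to be computed. The exposure is limited to decisions to stop, halt or amend; type I error and outcome scoring are not implicated. This should be fixed, but it does not invalidate the primary comparison. Confidence is medium, because the timing and form of the release are not stated.

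**What to change.** **Section 8.1.** Replace the sentence on who knows the one-year finding with: *Before database lock, only the designated unblinded biostatistician may know the one-year between-arm comparison; it will not be released to the sponsor or other study personnel before then, by arm or by code A or B.*

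**Section 14.4.** After the sentence on Sponsor blinding, add: *For the Sponsor, this blinding also covers between-arm caries summaries, whether labelled by arm or by code A or B.*

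Keep the 0.025/0.025 split. The biostatistician need not be barred from running the comparison before lock; withholding it from the sponsor is enough.

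**Cost.** Two wording changes, with no effect on sample size, visits or significance levels. The sponsor loses early knowledge of the one-year result, for which the protocol states no use. The alternative is to restore the interim section and state the recipient, date, form and permitted use. That would also reconcile the text, but it would leave the Sponsor/Investigator exposed to the trend.
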